⁷The EORTC QLQ-C30 is a well-validated quality-of-life assessment for patients with cancer, consisting of 30 questions that encompass three symptom scales (pain, fatigue, and nausea/vomiting) and six questions about single symptoms, as well as five functional scales (physical, cognitive, role, emotional, and social) and one scale assessing global health status/quality of life. Each scale consists of two to five items, and all items have four response categories (not at all, a little, quite a bit, and very much), except for two items assessing overall health status/quality of life, which use a 7-point scale.

⁸In addition to clinician assessment of adverse effects according to CTCAE v4.03, adverse effects related to the use of dexamethasone, such as heartburn (F, S), nausea (F, S), pain in the abdomen (F, S, I), vomiting (F, S), arm/leg swelling (F, S, I), fatigue (F, I), decreased appetite (S, I), anxiety (F, SI, I), feelings that nothing could cheer you up (F, S, I), insomnia (S, I), sad or unhappy feelings (F,S, I), hiccups (F, S), hives (P), itchy skin (S), and rash (P) will be rated by patients using the PRO-CTCAE, which has recently been translated and validated in Spanish (Arnold *et al.* 2016, Basch *et al.* 2014, Bennett *et al.* 2016, Dueck *et al.* 2015). F = frequency, S = severity, I = interference with usual or daily activities, P = presence.

⁹Patients will be asked about their dyspnea (worse, about the same, or better) to compare the level of dyspnea before and after the study (Guyatt *et al.* 1993, Redelmeier *et al.* 1996).

¹⁰We will assess adherence by pill count on day 7 and day 14. We will also examine the success of blinding by asking patients to guess which treatment was given (“dexamethasone,” “placebo,” or “do not know”).

¹¹If patient available, otherwise, a phone call or other remote method will be conducted to administer the questionnaires.

E. Statistical Analysis

E.1. Sample size calculation. We will use 2:1 randomization as outlined in Section D.1.2.8. With a two-sided 5% alpha, normally distributed data, equal variance between treatment groups, and a within-group standard deviation of 2.0 (based on our preliminary data; Section D.1.1.3), we will need a total of 174 (116 + 58) patients to have 80% power to detect a mean difference of 1.0 between treatment groups. Assuming 15% attrition, we will need to enroll 134 patients in the dexamethasone arm and 67 in the placebo arm (201 total).

E.2. Data analysis

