
Table 1. Change in dyspnea in the dexamethasone and placebo arms (statistically significant values in boldface type)

| Variable | Dexamethasone | | | Placebo | | | Mean difference between arms (95% CI) |
|---|---------------|-------------|--|---------|-------------|--|---------------------------------------|
| | N | Mean (SD) | Mean change from baseline (95% CI) | N | Mean (SD) | Mean change from baseline (95% CI) | |
| ESAS dyspnea (average over the past 24 hours) | | | | | | | |
| Baseline | 19 | 5.0 (2.1) | - | 19 | 4.7 (1.5) | - | - |
| Day 4 | 15 | 3.3 (1.8) | -1.9 (-3.3 to -0.5), P = 0.01 | 15 | 3.7 (2) | -0.7 (-2.1 to 0.6), P = 0.38 | -1.2 (-3 to 0.6) |
| Day 7 | 16 | 3.6 (2.6) | -1.8 (-3.2 to -0.3), P = 0.02 | 14 | 3.3 (2.1) | -1.3 (-2.4 to -0.2), P = 0.03 | -0.5 (-2.2 to 1.2) |
| EORTC Quality of Life Questionnaire-C30 Dyspnea (over the past week) | | | | | | | |
| Baseline | 19 | 57.9 (29.1) | - | 19 | 49.1 (20.4) | - | - |
| Day 4 | 15 | 46.7 (16.9) | -15.6 (-29.3 to -1.8), P = 0.04 | 15 | 46.7 (24.6) | 0 (-14 to 14), P > 0.99 | -15.6 (-33.5 to 2.3) |
| Day 7 | 16 | 47.9 (17.1) | -10.4 (-21.1 to 0.3), P = 0.08 | 13 | 43.6 (16) | -5.1 (-19 to 8.8), P = 0.69 | -5.3 (-21.2 to 10.6) |

D. Experimental Approach

D.1. Overall Study design. This is a parallel, two-arm, double-blind, randomized, placebo-controlled trial of dexamethasone for cancer patients with dyspnea (Figure 2). We plan to enroll 201 patients (134 in the dexamethasone group and 67 in the placebo group, Section D.1.11.1), with a target enrollment rate of five to six patients per month. The eligibility criteria are shown in Table 2. After providing written informed consent, enrolled patients will complete baseline questionnaires to assess the severity of their dyspnea. Study drug may be mailed to participants. At MD Anderson, sometimes patients do not have time to pick up study medication after enrollment and do not start the study until a few days later. For HHS/LBJ, patients will get their medication via MD Anderson pharmacy so their medications will also need to be mailed to them. On the basis of our experience, we believe that the proposed study is feasible and will not add an undue burden for patients. The rationale for the proposed study design is as follows.

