D.1.6. Open label phase. This will offer all patients the opportunity for a trial of the active agent, which may enhance the rate of recruitment. It will also allow us to taper the corticosteroid dose slowly and to explore longer-term use of corticosteroids beyond 2 weeks.

D.1.7. Placebo control. The use of placebo control is justified because definitive evidence to suggest that dexamethasone is superior to placebo remains lacking (i.e., clinical equipoise). Patients in either study arm will have access to other contemporary treatments if already scheduled (e.g., opioids, bronchodilators). Because the primary outcome measure is a patient-reported outcome, placebo control is essential. Indeed, our previous research studies have consistently shown that a placebo offers clinically significant benefits with minimal harm (Bruera *et al.* 1993, Bruera *et al.* 2007).

D.1.8. Randomization in 2:1 ratio. The 2:1 ratio was elected to maximize the number of patients available for response predictor analysis (Aim 2) and to help to improve our chances of recruitment. On the basis of our preliminary data favoring dexamethasone, we believe this ratio is justified.

D.1.9. Selection of putative predictive markers.

D.1.9.1 Inflammatory biomarkers. Dexamethasone is hypothesized to modulate the inflammatory response to help treat dyspnea. We have selected IL-1 β , IL-6, IL-8, IL-10, and TNF- α for their specific relevance to dyspnea on the basis of our literature review.

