| 3. Previous allergic reactions to dexamethasone |
| 4. Diagnosis of diabetes mellitus uncontrolled with oral hypoglycemic agents or insulin |
| 5. Postsurgical open wound that has not healed at the time of enrollment |
| 6. Any infection requiring antibiotics at the time of study enrollment |
| 7. Major surgery within the past 2 weeks |
| 8. Megestrol use at the time of study enrollment |
| 9. Neutropenia (absolute neutrophil count $<1.0 \times 10^9/L$) at the time of study enrollment (bloodwork is not required if patient did not have chemotherapy within past 2 weeks) |
| 10. Currently receiving or expected to start cytotoxic chemotherapy or immunotherapy within 1 week of study enrollment and additional dexamethasone cannot be used concurrently as per attending oncologist |
| 11. Severe anemia (hemoglobin <8 g/L) not corrected prior to study enrollment (bloodwork is not required if patient did not have chemotherapy within past 2 weeks) |
| 12. COPD exacerbation at the time of study enrollment |
| 13. Heart failure exacerbation at the time of study enrollment |
| 14. Expected to undergo therapeutic thoracentesis in the next 2 weeks |
| 15. High anxiety score ($\geq 15/21$) on the Hospital Anxiety and Depression Scale (HADS) |
| 16. Chronic systemic corticosteroid use (>14 days) at the time of study enrollment |
| 17. Any expected corticosteroid use during study enrollment at higher doses than will be used in this study |

D.3. Recruitment. The research staff will screen patients in the outpatient setting to identify potential candidates. For patients who are eligible on the basis of chart review, our research staff will approach them either in-person, or through remote methods for permission to conduct further screening for eligibility. Remote methods will consist of phone or vetted video-conferencing platforms (WebEx, Skype, FaceTime, or Zoom) to call potential participants to explain the study and gauge interest. If the participant wishes to participate, MyChart or e-mail will be used to send the consent form and research staff will obtain consent through this method.

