D.5. Study interventions. Dexamethasone is a commonly used medication in cancer patients. It is approved by the US Food and Drug Administration for treatment of multiple indications, including allergic disorder (including asthma), cerebral edema associated with primary or metastatic brain tumor, craniotomy, or head injury, collagen disease, disorder of ear, disorder of endocrine system, disorder of eye, disorder of gastrointestinal tract, disorder of hematopoietic structure, disorder of respiratory system (treatment of berylliosis, fulminating or disseminated pulmonary tuberculosis (when used concurrently with appropriate antituberculosis therapy), idiopathic eosinophilic pneumonias and symptomatic sarcoidosis, Loeffler's syndrome not manageable by other means and aspiration pneumonitis), disorder of skin, exacerbation of multiple sclerosis, hypercalcemia of malignancy, idiopathic thrombocytopenic purpura, inflammatory disorder of musculoskeletal system, macular retinal edema, mycosis fungoides, neoplastic disease, palliative management of leukemias and lymphomas, nephrotic syndrome, Idiopathic or due to lupus erythematosus without uremia, non-infectious posterior uveitis, trichinosis with neurologic or myocardial involvement, tuberculosis of meninges with subarachnoid block or impending block when used concurrently

with antituberculosis therapy. However, it has not been specifically approved for management of dyspnea.

Our study proposes to use oral dexamethasone for the management of dyspnea. Based on our preliminary data, the intervention arm will receive dexamethasone at a dose of 8 mg given orally twice daily for 7 days, then 4 mg given orally twice daily for 7 days. We do not plan to seek FDA approval for the new indication of dyspnea.

The control arm will receive placebo capsules prepared by a compounding pharmacy (e.g. Greenpark Pharmacy) identical in appearance to dexamethasone 4 mg capsules, and will be instructed to take two capsules twice a day for 7 days, followed by one capsule twice a day for 7 days.

In the open label phase, patients assigned to either arm will be asked to take dexamethasone 4 mg orally twice a day for 7 days, then 2 mg orally twice a day for 7 days. Both dexamethasone and placebo capsules used throughout this study will be dispensed by Investigational Pharmacy at MD Anderson. Dexamethasone/placebo capsules and open-label tablets will be provided free of charge to patients during the study period.

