D.8. Medication use during study and cointerventions. During the 2-week blinded phase, patients may continue their usual treatments for dyspnea, including opioids, supplemental oxygen, and bronchodilators. These treatments will be documented and adjusted for in the analysis. Our eligibility criteria are designed to specifically exclude patients who have reversible causes of acute dyspnea, such as pleural effusions, COPD exacerbations, or pneumonia.

D.9. Research staff training. An orientation will be held with research staff involved in this study to introduce them with the study design, and standardize the provision of each intervention. We will also conduct principal investigator research meetings 2-4x/month.

D.10. Patient Safety, Monitoring, and Confidentiality. Prior to study initiation, all research staff participating in this study will receive an orientation to the devices and forms in this study to ensure consistent assessments. During the study, trained research staff will be performing study assessments and monitoring the patient carefully throughout the study period. In addition to daily phone calls, or contact through other remote methods, patients will be given the contact information of the research staff in case they develop any significant adverse effects, and will be treated as they arise as per clinical practice. The study may be discontinued at the discretion of the treating physician or study principal investigator. Regulatory monitoring will be provided by the principal investigator, the Institutional Review Board, and the Data Safety

and Monitoring Board. Patient confidentiality will be ensured by use of patient initials, secure storage of clinical data, and anonymous reporting.

Table 3. Study assessments

| Assessment | Baseline (in person) | Days 0-6 (phone or remote contact) | Day 7±2 (in per- son ¹¹) | Days 8- 13 (phone or re- mote contact) | Day 14±2 (in per- son ¹¹) | Day 28±2, Day 42±2 (phone or remote contact) |
|--|-------------------------|---|--|---|--|--|
| Screening (Appendix A, B) | ✓ | | | | | |
| Demographics (Appendix C) | ✓ | | | | | |
| Dyspnea NRS score (primary outcome: intensity; secondary: unpleasantness; assessment requires <1min) ¹ (Appendix D) | ✓ | ✓ | ✓ | ✓ | ✓ | ✓ |
| Personalized dyspnea goals (<1min) ² (Appendix I) | ✓ | | | | ✓ | |
| Biomarkers (blood draw, 15min) ³ (Appendix J) | ✓ | | ✓ | | ✓ | |

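### For chemotherapy or immunotherapy not yet started, exclusion 10 looks only 1 week past enrollment, while study dexamethasone may start days later and run for up to 4 weeks

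*Combined protocol and SAP*

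**What the plan says.** Exclusion 10 in Table 2 applies to a patient "Currently receiving or expected to start cytotoxic chemotherapy or immunotherapy within 1 week of study enrollment and additional dexamethasone cannot be used concurrently", as judged by the attending oncologist. It has two limbs: therapy already under way, and therapy expected to start within a week of enrollment. Either limb excludes only if the oncologist also rules out added dexamethasone.

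The drug exposure that this criterion guards is described elsewhere:

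- **Start of dosing.** Section D.1 says that some patients at the main site "do not start the study until a few days later", and that drug for the county-hospital site has to be mailed. It gives no length for the delay.
- **Blinded phase.** Section D.5 gives the active arm "8 mg given orally twice daily for 7 days, then 4 mg given orally twice daily for 7 days".
- **Open-label phase.** Section D.5 says "patients assigned to either arm will be asked to take dexamethasone 4 mg orally twice a day for 7 days", then 2 mg twice a day for 7 more days. Section D.1.6 presents this phase as a way to "offer all patients the opportunity for a trial of the active agent".
- **Safeguards during treatment.** Section D.10 says "The study may be discontinued at the discretion of the treating physician or study principal investigator". It also says "In addition to daily phone calls, or contact through other remote methods, patients will be given the contact information of the research staff" in case of significant adverse effects.
- **Schedule.** Table 3 ticks screening at baseline only. The one assessment ticked for the daily contacts (days 0-6 and 8-13) is the dyspnea NRS. No contact is listed between day 14±2 and day 28±2.

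**The concern.** By including exclusion 10, the protocol accepts that some anticancer therapy should not be combined with study dexamethasone. The rule does not span the dosing it is meant to guard. Its clock starts at enrollment rather than at first dose, and it stops after 7 days, although dexamethasone can be given for up to 28 days. For therapy due on day 8 or later, the oncologist's objection plays no part in eligibility, because the timing condition has already failed.

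What is at stake is participant safety. A patient in the active arm could be taking dexamethasone when therapy begins that the patient's own oncologist considers incompatible with it. In the placebo arm this can happen only if the open-label offer is taken up. Because assignment is blinded, the clinicians cannot readily tell whether such a patient is on a steroid. Section D.1.4 also explains that the dose is tapered to limit adrenal suppression, so a conflict found mid-course is harder to handle than one found beforehand.

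**Working it through.** The plan states no figure to reproduce here, so the check is a count of days and doses.

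**Inputs**

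- Enrollment is day 0. The exclusion 10 window runs through day 7, so the first uncovered start is day 8 (Table 2).
- First dose is on day f. D.1 does not quantify the delay. Table 3 labels the first week of contacts as days 0-6, which supports f = 0. The values f = 3 and f = 5 are assumptions for a few days' delay.
- Blinded active dosing is 16 mg/day for 7 days, then 8 mg/day for 7 days (D.5). Total: 7 × 16 + 7 × 8 = 168 mg on days f to f + 13.
- Open-label dosing is 8 mg/day for 7 days, then 4 mg/day for 7 days (D.5). Total: 7 × 8 + 7 × 4 = 84 mg on days f + 14 to f + 27.

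**Formulas**, for incompatible therapy starting on day s, with s ≥ 8

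- Overlapping blinded days = max(0, f + 14 − s). The maximum, at s = 8, is f + 6.
- Of these, days at 16 mg/day at s = 8 = max(0, f − 1).
- Overlapping blinded dose at s = 8: 6 × 8 = 48 mg for f = 0, and 56 + 16(f − 1) mg for f from 1 to 8.

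**Results (maximum, s = 8)**

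| First dose, day f | Blinded days | Overlap, of 14 days | At 16 mg/day | Dose, of 168 mg |
|---|---|---|---|---|
| 0 | 0-13 | 6 | 0 | 48 mg (29%) |
| 1 | 1-14 | 7 | 0 | 56 mg (33%) |
| 3 (assumed) | 3-16 | 9 | 2 | 56 + 32 = 88 mg (52%) |
| 5 (assumed) | 5-18 | 11 | 4 | 56 + 64 = 120 mg (71%) |

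The overlap shrinks quickly when therapy starts later. For f = 0, a day 11 start overlaps 14 − 11 = 3 blinded days, and a day 14 start overlaps none. For f = 1, the same starts overlap 4 days and 1 day.

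The open-label course begins on day f + 14, so for every f all 14 of its days (84 mg) lie beyond day 7, in either arm, if it is taken up.

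**Does another provision close the gap?** Exclusion 17 concerns corticosteroids at doses above those in the study, not new anticancer therapy. Section D.8 covers usual dyspnea treatments. The D.10 stop names no trigger tied to new chemotherapy or immunotherapy. Nothing in the available text asks the exclusion 10 question again.

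**The case against.** The strongest reply is that the affected group is small and that its gatekeeper already holds the remedy. The patient must have a new start on day 8 or later, the oncologist must object, and the overlap must still occur. The clinician who objects would normally be the one starting the therapy, and D.10 lets the treating physician stop the study. Exclusion 10 rests on clinical judgment too, so calling the stop discretionary does not by itself make it weak. D.5 and D.10 promise daily contact and careful monitoring, and Table 3 places adverse-effect review at day 7±2 and day 14±2. A window that roughly matches the 16 mg/day week can also be defended, since D.2 aims for broad generalizability.

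Most of this stands, and it keeps the point modest. It does not remove it, because none of these provisions makes anyone ask about newly planned therapy.

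Three stronger readings are tempting, and the documents do not support them:

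- **That the primary analysis is threatened.** With prompt dosing, the 16 mg/day week and, largely, the day 7 assessment fall inside the present window. A delay moves part of them outside, but nothing shows how many patients would be affected.
- **That the overlap percentages measure risk.** They are upper limits for one affected active-arm patient whose therapy starts exactly on day 8, and the larger ones rest on assumed delays. The documents name no specific harm.
- **That no recheck exists anywhere.** Figure 2 and the appendix forms are not in the available text, so a recheck there cannot be ruled out.

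**Conclusion.** The point holds as a modest safety gap that should be corrected. For therapy not yet started, a patient with an oncologist's objection and a start due on day 8 or later is eligible as written. The most that can overlap in the blinded phase is 6 of 14 days (48 mg) with first dose on the day of enrollment, or 7 days (56 mg) with first dose the next day. Each further day of delay adds one day at 16 mg/day. The whole 84 mg open-label course, if taken, is also outside the window.

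These counts assume that 1 week means through day 7 after enrollment and that dosing follows the D.5 schedule without interruption. Confidence is medium, because the number of patients affected is unknown and the missing forms could contain a further check.

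**What to change.** 1. Count the exclusion 10 window from the planned first dose, and make it cover at least the 7 days at 16 mg/day up to the day 7 endpoint.
2. Ask the same question again at the existing day 7±2 contact, looking ahead over blinded week 2.
3. Ask it once more at the day 14±2 contact, before open-label drug is given, looking ahead over the open-label course.
4. If incompatible therapy is ongoing or due, the treating physician and the oncologist stop or shorten the course. Any taper treats the patient as possibly steroid-exposed, because assignment is blinded.

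If an appendix form already asks this, Table 2 and Table 3 need only be aligned with it.

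Extending the exclusion itself to 14 days from first dose is an acceptable alternative. Exclusion 14 already uses a 2-week look-ahead, so the question is practical at screening. The price is losing some patients whose conflict arises only in blinded week 2 and who could have supplied day 7 data. A 4-week exclusion at enrollment is not needed.

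The cost is reworded text for one criterion, one question at two existing contacts (either of which may be remote), and some coordination with the oncologist when the answer is yes. A few patients whose own oncologist objects would not be enrolled or would stop early. Where drug is mailed, the planned first-dose date may be uncertain at screening and should be confirmed when dosing starts.

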D.1.9.2. Pulmonary function. A large proportion of patients with cancer have restrictive lung disease (Hui *et al.* 2016a). In the fibrotic interstitial lung disease setting, there is evidence to support the use of corticosteroids for dyspnea (Bajwah *et al.* 2013). Thus, restrictive lung disease may be a predictive marker. Cachexia, a common syndrome in patients with advanced cancer, is associated with decreased respiratory muscle function (Coats 2002, Remels *et al.* 2013, Roberts *et al.* 2013), which in turn may be associated with dyspnea (Chiu *et al.* 2004, Travers *et al.* 2008). Indeed, short-term corticosteroids have been reported to have a positive impact on muscle strength in patients with various inflammatory disorders (Manzur *et al.* 2008, Sunderkotter *et al.* 2016). Mechanistically, a positive association between dyspnea response to dexamethasone and pulmonary function (i.e., baseline or change) would suggest that the therapeutic effect of corticosteroids on dyspnea is mediated peripherally, and a lack of association may imply more a central effect.

D.1.9.3. Baseline dyspnea function. Studies from our group and others consistently demonstrated that a high baseline symptom score is associated with a greater likelihood of response to both active intervention and placebo (De La Cruz *et al.* 2010, Hui *et al.* 2015b). Thus, the randomization scheme will stratify by this variable. We will also adjust for this variable in our statistical analysis.

D.2. Eligibility criteria (Table 2). We designed these criteria to maximize the study's generalizability. We will be stratifying by baseline dyspnea intensity and study site. We also

considered stratifying by other factors such as pulmonary function and inflammatory markers, but no other factors have been consistently found to be predictive markers at this time in cancer patients.

| Table 2. Study eligibility criteria |
|---|
| Inclusion criteria |
| 1. Diagnosis of cancer |
| 2. Dyspnea with an average intensity ≥ 4 on the dyspnea NRS (range 0-10) over the past week |
| 3. Seen at an outpatient clinic at MD Anderson Cancer Center or LBJ Hospital General Oncology Clinic |
| 4. Able to communicate in English or Spanish |
| 5. Karnofsky performance status $\geq 30\%$ |
| 6. Age 18 years or older |
| Exclusion criteria |
| 1. Delirium (i.e., score >13 on the Memorial Delirium Assessment Scale; range 1-30) |
| 2. Oxygen saturation $<90\%$ despite supplemental oxygen >6 L/minute |

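### The severe-anemia exclusion pairs a number with a unit that does not fit it: hemoglobin <8 g/L is <0.8 g/dL (minor correction)

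*Combined protocol and SAP*

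**What the plan says.** Table 2 in section D.2 lists, as exclusion 11, "Severe anemia (hemoglobin <8 g/L) not corrected prior to study enrollment". The same line adds in parentheses that "bloodwork is not required if patient did not have chemotherapy within past 2 weeks". No other place in the documents gives a hemoglobin value, in this unit or another.

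The other laboratory cut-off in the table, exclusion 9, also uses a per-litre unit: "Neutropenia (absolute neutrophil count $<1.0 \times 10^9/L$) at the time of study enrollment". It carries the same bloodwork waiver.

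The criteria apply to ambulatory patients: "Seen at an outpatient clinic at MD Anderson Cancer Center or LBJ Hospital General Oncology Clinic", with "Karnofsky performance status" of at least 30%.

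Section D.8 gives the general aim: "Our eligibility criteria are designed to specifically exclude patients who have reversible causes of acute dyspnea". Its examples are pleural effusions, COPD exacerbations and pneumonia. Anemia is not among them, although the list is open-ended. The documents state no purpose for exclusion 11 itself.

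**The concern.** A threshold in an eligibility table is an instruction. Someone screening a chart compares a laboratory value with the number and unit on the page, and an auditor later does the same. Here the number contradicts the words around it. The criterion is labelled as severe anemia and applies when the anemia has not been corrected before enrollment, so it presupposes that some candidates will meet it. A cut-off of 0.8 g/dL is not one that outpatients could be expected to meet.

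Two things are at stake. If the line is applied as printed, a patient whom the label describes passes the numeric test. If staff silently substitute another unit, enrollment decisions depart from the approved text, and different staff or sites have no written figure to agree on.

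**Working it through.** **Inputs.** The cut-off is <8 g/L (Table 2, exclusion 11). The conversion is 1 g/dL = 10 g/L. The documents give no hemoglobin distribution, so 4 to 12 g/dL (40 to 120 g/L) is assumed as an illustrative range for ambulatory patients.

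**Step 1: convert the written cut-off.** The figure is a stated threshold and not a derived one, so there is no calculation in the plan to reproduce.

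- As written: 8 g/L ÷ 10 = 0.8 g/dL.
- The same digit on the g/dL scale: 8 g/dL × 10 = 80 g/L.
- Ratio of the two readings: 80 ÷ 8 = 10.

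**Step 2: apply both readings over the assumed range.** The g/dL column only shows how far the readings diverge. It is not a statement of what the threshold should be.

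| Hemoglobin, g/dL | Same value, g/L | Excluded by <8 g/L as written | Excluded if the unit were g/dL |
|---|---|---|---|
| 4 | 40 | no | yes |
| 5 | 50 | no | yes |
| 6 | 60 | no | yes |
| 7 | 70 | no | yes |
| 7.9 | 79 | no | yes |
| 8 | 80 | no | no |
| 9 | 90 | no | no |
| 10 | 100 | no | no |
| 12 | 120 | no | no |

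The literal rule excludes no value in the range. At the bottom of it, 40 ÷ 8 = 5, so a patient at 4 g/dL is five times above the written cut-off. The two readings give different decisions for every value from 8 g/L up to just under 80 g/L.

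**Step 3: see whether the rest of the table explains the unit.** The neutrophil cut-off in exclusion 9 is also per litre and is plausible as written. The problem is therefore confined to the hemoglobin line.

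**Step 4: see whether the main analysis depends on it.** The sample size in section E.1 rests on these assumptions: "With a two-sided 5% alpha, normally distributed data, equal variance between treatment groups, and a within-group standard deviation of 2.0", with a mean difference of 1.0, 80% power and 15% attrition. The primary model in E.2.1 compares day 7 scores adjusted for baseline. Hemoglobin enters neither.

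**The case against.** The strongest reply is that the line opens by naming the condition and the parenthesis only puts a number on it. The mismatch is conspicuous, and a trained screener would probably notice it and not apply 0.8 g/dL. That stands. A reader might infer from the printed figure that the exclusion does nothing in practice and that severely anemic patients were enrolled. The documents do not show this; they show only that the written number cannot do the work its label describes.

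The bloodwork waiver is a second fair point. Hemoglobin need not be measured in patients without chemotherapy in the past 2 weeks, so the unit is not the only limit on the criterion, and correcting it would not ensure that such patients are screened out.

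A reader might also infer that a safety safeguard, or a protection against confounding, has failed, and that anemic patients transfused during follow-up would add noise to the dyspnea NRS. The documents give no such purpose for exclusion 11 and no anemia prevalence, transfusion rate or effect on the NRS. Any such patients would also enter before randomization and so, in expectation, affect both arms alike. An anemia exclusion is consistent with the aim in D.8, but the support goes no further.

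Finally, the text was extracted by a program, and a single lost letter would produce this unit. That cannot be excluded from the text alone. However, the unit is legible and the neighbouring per-litre unit reads sensibly, so there is no positive sign of an artefact. Comparison with the source file would settle it.

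**Conclusion.** The point holds as a unit error in an operative eligibility threshold. The written cut-off equals 0.8 g/dL, does not fit its own label, and is not restated correctly anywhere else. The two readings differ tenfold.

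That the literal cut-off excludes nobody rests on the assumed range of 4 to 12 g/dL, not on trial data. The share of candidates affected is unknown, and so is the size of any effect on the NRS. The sample size and the primary analysis stand as they are. Severity is minor: the line is wrong as written and worth correcting, but no demonstrated consequence follows for the trial's conclusions.

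**What to change.** The clinical team should confirm the intended threshold. Exclusion 11 should then be rewritten so that figure and unit agree, in the unit that the site laboratories report. No value is proposed here.

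The screening form should be checked for the same error. Table 3 refers to it as Appendix A and B, which were not available, so it may already be correct. If eligibility is also checked electronically, that check should match; the documents do not describe one.

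The cost is a correction to one line of the protocol, plus the same change in the form if it is needed. No change to the analysis plan or the sample size follows.
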